4. STUDY DESIGN

4.1. Overall Design

This is a Phase I, first-time-in-human (FTIH), randomized, double-blind (sponsor unblinded), single-center, placebo-controlled, dose-escalation study to determine the safety, tolerability, and pharmacokinetic (PK) profile of GSK3342830 after administration of single (Part 1) and repeat (Part 2) IV doses in healthy adult subjects, and after administration of a single IV dose in healthy adult Japanese subjects (Part 3). Part 1 will investigate escalating single IV doses of GSK3342830. Part 2 will investigate escalating repeat IV doses of GSK3342830 with repeat dosing for 14 days and multiple dosing per day for 13 days as follows: a single IV infusion on Day 1, TID IV infusions on Days 2 through 14 (approximately every 8 hours), and a single IV infusion on Day 15. Part 3 will investigate a single IV dose of GSK3342830 in Japanese subjects.

For Parts 1 and 2, on Day 1, before study drug administration, subjects who meet the criteria for study entry will be assigned to the current dose level cohort and randomized to receive GSK3342830 or placebo. For Part 3, on Day 1, before study drug administration, subjects who meet the criteria for study entry will be randomized to receive GSK3342830 or placebo. All doses of GSK3342830 or placebo are planned to be administered as a 1-hour infusion.

This is the first administration of GSK3342830 in humans; therefore, the study design may change based on emerging data from each cohort. As preliminary safety, tolerability,

and PK results are reviewed internally at GSK and with the clinical study site, the following adjustments may be made to the proposed study design:

- The proposed dose levels, dosing frequency, infusion duration, and/or infusion volume of GSK3342830 may be adjusted during the course of Part 1 and/or Part 2 of the study.
- The duration of repeat dose administration planned for Part 2 may be adjusted.
- Cohorts may be added to or removed from either study Part 1 or Part 2 depending on findings from previous cohorts.
- Pharmacokinetic sampling and/or study assessment schedules may be changed.

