In Part 1, subjects will remain confined to the clinical unit from admission on Day –1 until all scheduled safety and PK assessments have been completed on Day 3. The duration of study (from Screening to the Follow-up visit) for each subject will be up to approximately 43 days.

[figure not shown]
Part 2: Repeat Dose Escalation in Healthy Subjects

Part 2 is planned to include a sequential panel of up to 3 dose level cohorts. Additional repeat dose cohorts may be evaluated to further assess the safety, tolerability, and pharmacokinetics of GSK3342830. The planned starting GSK3342830 dose in Part 2 is 1000 mg administered as a single IV infusion on Day 1, TID IV infusions on Days 2, 3, 4, 5, 6, 7, 8, 9, 10, 11, 12, 13, and 14, and a single IV infusion on Day 15. The dose is planned to increase in subsequent cohorts to 2000 and 4000 mg TID as shown in [Figure 2](#). The starting dose and maximum dose may be changed based on clinical safety and PK findings in Part 1 or earlier doses in Part 2 and consideration of the AUC(0-24) and Cmax exposures based on the NOAEL.

On Day 1, before study drug administration, subjects will be randomized to treatment with either GSK3342830 or placebo in a 4:1 ratio. Study assessments will be performed as indicated in the Time and Events Tables (Section 7.1).

Doses are planned to escalate in a sequential fashion based on the preliminary safety, tolerability, and PK data from Part 1 and at least 14 days of repeat dosing in approximately 5 subjects who received active treatment in the previous cohort in Part 2. The evaluated subjects should be followed for a minimum of 24 hours after dosing on Day 15. The dosing frequency, duration of dosing, and decision to dose in the next dose level may be changed based on the safety, tolerability, or PK findings in Part 1 or earlier doses in Part 2.

Figure 2 Part 2 Repeat Dose Escalation Study Design Schematic

Note: Figure shows illustration of the planned doses, which may be switched, changed, or cancelled based on preliminary safety, tolerability, and pharmacokinetic data from preceding cohorts.

The following rules will guide dose selection in Part 2:

- The starting daily dose in Part 2 will be selected such that its predicted AUC(0-24) and C_{max} on the last day of dosing (i.e., account for any drug accumulation) is no higher than the exposure of a dose that has been found to be safe and well tolerated in Part 1.

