4.3. Type and Number of Subjects

For Part 1, approximately 48 healthy adult subjects will be enrolled with approximately 8 subjects in each of the 6 planned cohorts. In each Part 1 cohort, approximately 6 subjects will be assigned to active treatment and approximately 2 subjects will be assigned to placebo. For Part 2, approximately 30 healthy adult subjects will be enrolled with approximately 10 subjects in each of the 3 planned cohorts. For Part 3, approximately 10 healthy adult Japanese subjects will be enrolled. In each Part 2 cohort and the Part 3 cohort, approximately 8 subjects will be randomized to receive active treatment and approximately 2 subjects will be randomized to receive placebo.

Additional subjects/cohorts may be enrolled to allow for evaluation of additional dose levels.

Decisions regarding replacement of subjects prematurely discontinued from study drug in any cohort will be made by the investigator and the GSK medical monitor on a case-by-case basis. Subjects may only be randomized to one cohort and may only participate in one part of the study.

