4.5. Dose Justification

Dose selection of GSK3342830 for this FTIH study was based on NOAEL data from animal toxicology studies, predicted pharmacokinetics for humans using PK data from preclinical species, and a targeted therapeutic exposure based on efficacy data from a rat pneumonia model. GSK3342830 is a catechol cephalosporin antibiotic that utilizes the bacterial iron transport system to facilitate transport into bacteria and disrupts the synthesis of the peptidoglycan layer of bacterial cell walls. This is not a human target; therefore, the minimum anticipated biological effect level in humans for GSK3342830 was not determined.

As described in the following sub-sections,

- While the maximum recommended starting dose is 1935 mg, the proposed starting dose is 250 mg, which is predicted to have AUC(0-t) and C_{max} values 45-fold and 83-fold lower than the NOAEL values, respectively.
- The predicted dose to achieve the therapeutic exposure target ranges from 500 to 2000 mg, which is predicted to have AUC(0-t) values 5.6- to 22-fold lower and C_{max} values 10- to 42-fold lower than the NOAEL values after administration of single doses, and AUC(0-24) values 1.9- to 7.5-fold lower and C_{max} values 10- to 42-fold lower than the NOAEL values after administration of repeat doses.
- The anticipated maximum 6000 mg single dose will provide an AUC exposure of 1933 h•µg/mL (predicted AUC encompassing 95% of the simulated population) with a safety margin of 1.48-fold and a C_{max} of 849 µg/mL (predicted C_{max} encompassing 95% of the simulated population) with a safety margin of 2.67-fold.
- The anticipated maximum 4000 mg TID dose will provide an AUC exposure of 3846 h•µg/mL (predicted AUC[0-24] encompassing 95% of the simulated population) that may exceed the systemic NOAEL AUC(0-24) exposure of 2875 h•µg/mL (safety margin of 0.93-fold) and a C_{max} of 569 µg/mL (predicted C_{max} encompassing 95% of the simulated population) with a safety margin of 3.98-fold.
- Based on a concentration limitation of 25 mg/mL, IV solution volumes between 100 to 250 mL would support single doses of 2500 to 6000 mg (IV formulation work is ongoing. Formulation instructions will be available in the Pharmacy Manual before the start of the study).
- Importantly, dose escalation decisions will be based on observed exposure, safety, and tolerability data for GSK3342830 from the previous dose level.

Data Used for Dose Justification

No observed adverse effect level (NOAEL)

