6.3. Planned Dose Adjustments

- This protocol allows some alteration from the currently outlined dosing schedule. The maximum daily dose is planned to not exceed 6000 mg in Parts 1 and 3, and 4000 mg in Part 2.
- The decision to proceed to the next dose level of GSK3342830 will be made by the GSK study team and the investigator based on preliminary safety, tolerability, and PK data obtained in approximately 4 subjects for Part 1 and approximately 5 subjects for Part 2 that received active study treatment in the prior dose level. The actual doses to be administered may be adjusted based on the preliminary safety, tolerability, and PK data at previous dose levels; these dose adjustments may involve either an increase or a decrease in the planned dose. A schematic of the planned study design is presented in [Figure 3](#).

- The dosing schedule may also be adjusted to expand a dosing cohort to further evaluate safety and PK findings at a given dose level, or to add cohorts to evaluate additional dose levels. The study procedures for these additional subject(s) or cohort(s) will be the same as those described for other study subjects.
- If AEs, which are of severe intensity or greater and are consistent across subjects in a given dose level, or if unacceptable pharmacological effects, reasonably attributable in the opinion of the investigator to dosing with GSK3342830, are observed in 2 or more subjects in a dose level, further dose escalation will be temporarily halted and no further subject in subsequent cohorts will be dosed until a full safety review of the study has taken place. Relevant reporting and discussion with the medical monitor, relevant GSK personnel, and with the Ethics Committee will then take place before any resumption of dosing.
- If the same SAE occurs in more than 1 subject, further dose escalation will be temporarily halted and no further subject in subsequent cohorts will be dosed until a full safety review of the data has taken place.
- The previously mentioned criteria will apply even if measured PK parameters are below the PK stopping criteria, and every effort will be made to take a blood sample at the time of the event for PK analysis in the presence of any of the above events.

Figure 3 Planned Study Schematic

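### Protocol Section 6.3 gives 4000 mg as the planned maximum daily dose in Part 2, but the planned 2000 and 4000 mg TID cohorts receive 6000 and 12000 mg/day; 4000 mg is the per-infusion maximum

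*Protocol*

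**What the plan says.** On the limit, Protocol Section 6.3 reads: "The maximum daily dose is planned to not exceed 6000 mg in Parts 1 and 3, and 4000 mg in Part 2".

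On the Part 2 regimen:

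- Protocol Section 4.2 starts Part 2 at 1000 mg, with one infusion on Day 1, three infusions a day on Days 2 to 14, and one on Day 15. It then says: "The dose is planned to increase in subsequent cohorts to 2000 and 4000 mg TID as shown in" Figure 2. Section 4.1 describes the same schedule as "multiple dosing per day for 13 days".
- Protocol Section 4.5 takes 4000 mg TID as the top of the range: "The anticipated maximum 4000 mg TID dose will provide an AUC exposure", followed by the predicted AUC(0-24).
- Protocol Section 6.1 lists Part 2 dosage levels of 1000, 2000 and up to 4000 mg, and gives the TID schedule separately in the dosing instructions. The levels are therefore amounts per infusion.
- SAP Section 2.3 and the treatment-group table in SAP Section 10.3.1 carry the same three TID cohorts.

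On flexibility, Section 4.1 says: "The proposed dose levels, dosing frequency, infusion duration, and/or infusion volume of GSK3342830 may be adjusted" during Part 1 and/or Part 2. Section 4.2 says of Part 2: "The dosing frequency, duration of dosing, and decision to dose in the next dose level may be changed" on emerging data. It also allows the Part 2 starting and maximum doses to change.

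**The concern.** A stated maximum is something a site, monitor or ethics committee can hold against the dosing record. Here the plan, followed exactly and with no alteration, goes over the stated Part 2 figure in two of its three cohorts. The sentence therefore cannot serve as a check on Part 2 dosing, and a literal reader could query every TID day in those cohorts.

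The section matters too. Section 6.3 governs upward and downward changes of dose, and this is a first administration in humans. A wrong number there carries more weight than one in background text.

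**Working it through.** **Inputs**

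- Stated Part 2 maximum daily dose: 4000 mg (Protocol 6.3).
- Planned amounts per infusion: 1000, 2000 and 4000 mg (Protocol 4.2, 6.1).
- Infusions per day: 3 on Days 2 to 14, and 1 on Days 1 and 15 (Protocol 4.2, 6.1).
- Active subjects: "approximately 8 subjects will be randomized to receive active treatment" in each Part 2 cohort (Protocol 4.3, approximate numbers).
- Predicted exposures: Protocol Appendix 9, Tables 8 and 9.

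**Can the stated figures be reproduced?** Daily dose = amount per infusion × infusions per day.

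- Parts 1 and 3: 6000 × 1 = 6000 mg. This agrees with Section 6.3.
- Part 2, Days 1 and 15, top cohort: 4000 × 1 = 4000 mg. This agrees, but only on those two days.
- Part 2, Days 2 to 14:

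| Planned cohort | Daily dose | Ratio to 4000 mg |
|---|---|---|
| 1000 mg TID | 3 × 1000 = 3000 mg | 0.75 |
| 2000 mg TID | 3 × 2000 = 6000 mg | 1.5 |
| 4000 mg TID | 3 × 4000 = 12000 mg | 3.0 |

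The Part 2 figure is not reproduced. TID dosing covers 13 of the 15 dosing days. The two higher cohorts hold about 2 × 8 = 16 of the 3 × 8 = 24 planned active subjects. A true limit of 4000 mg/day under TID dosing would allow 4000 / 3 ≈ 1333 mg per infusion, which would exclude both of those cohorts.

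**Is 4000 mg TID perhaps 4000 mg split over the day?** Compare the predicted AUC at the 5th, 50th and 95th percentiles (h•µg/mL):

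| Nominal dose | Single dose, Table 8 | TID AUC(0-24), Table 9 | Ratio |
|---|---|---|---|
| 1000 mg | 206, 259, 320 | 618, 777, 960 | 3.00 |
| 2000 mg | 409, 512, 640 | 1227, 1536, 1920 | 3.00 |
| 4000 mg | 820, 1026, 1282 | 2460, 3078, 3846 | 3.00 |

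The notes to Table 9 say that the repeat-dose values were derived from the single-dose simulation, so the factor of 3 is by construction. It is not independent pharmacokinetic evidence. It does show that the exposure justification counted three full infusions a day, which is 12000 mg/day at the top.

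**What does daily mean in this protocol?** The Part 2 selection rules in Section 4.2 tie the starting daily dose to predicted AUC(0-24), among other things. Section 4.1 says that a single 4000 mg dose should exceed the daily exposure of 1000 mg TID. In the tables that is a median of 1026 against 777, and 777 = 3 × 259. In both places daily refers to the 24-hour total.

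**The case against.** The strongest reply is that nobody would be misled. The sentence says planned, and it follows an opening that allows some alteration of the dosing schedule. Section 4.2 lets the Part 2 maximum change. The working controls are the selection rules, the NOAEL exposure targets, the Bayesian exceedance probabilities and the halting rules. The dosing instructions are unambiguous.

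The evident intent is also per infusion. The 4000 mg figure matches Section 6.1. The Section 4.2 rule that uses daily dose refers to Cmax as well as AUC(0-24). The rationale in Appendix 13 for editing this bullet speaks of the planned maximum dose without the word daily.

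Most of this stands, and it limits how much the point matters. It does not rescue the sentence. Permission to depart from a plan does not explain a limit that the unaltered plan exceeds. An intent that has to be recovered from other sections is a reason to correct the wording.

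A reader might infer more, in two ways:

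- *That the two higher cohorts are unauthorised, or that subjects could be misdosed.* The documents do not support this. Every section that specifies the regimen gives 4000 mg TID as the planned top level.
- *That the daily total is left open at other frequencies, so the protocol needs limits that hold whatever the frequency.* Section 4 does allow the frequency to change, but no section proposes anything other than TID in Part 2, and the AUC(0-24) targets in Section 4.2 already bear on daily exposure. Such a clause would be a new restriction found nowhere in the documents.

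**Conclusion.** The point holds as an internal inconsistency in a stated dose limit. The planned Part 2 daily doses on Days 2 to 14 are 3000, 6000 and 12000 mg against a stated 4000 mg, so the planned maximum is understated by a factor of 3.

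The consequence is small. The error is in the conservative direction and the intended regimen is clear elsewhere. No cohort is lost, and no escalation rule, stopping rule, estimate or analysis changes. The counts of 13 days and about 16 subjects show how much of Part 2 the sentence misdescribes. They do not measure harm, since those subjects would receive the intended regimen.

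The conclusion assumes that the cohort labels are amounts per infusion, which Section 6.1 and the factor of 3 between Tables 8 and 9 support, and that daily has its ordinary 24-hour meaning. It should be corrected because it sits in the operative dose-adjustment text of a first-in-human protocol and the correction is nearly free.

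**What to change.** In Protocol Section 6.3, replace the sentence with:

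*The maximum dose is planned to not exceed 6000 mg (single infusion) in Parts 1 and 3, and 4000 mg per infusion given TID (12000 mg per day) in Part 2.*

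This keeps the word planned, so the flexibility in Sections 4.1 and 4.2 is untouched, and it adds no restriction on other dosing frequencies. The cost is one sentence in one amendment. Cohorts, sample size, escalation rules and the SAP need no change.

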6.4. Blinding

This will be a double-blind (sponsor unblinded) study. The subjects will be completely blinded and the site staff will be blinded to subject-specific treatment assignment. The GSK study team will be unblinded at the aggregate level for decision making throughout the study (e.g. to support dose escalations and use of Bayesian predictive techniques). Where possible, the GSK/clinical research organization personnel will not have access to subject-specific treatment assignment so as to not potentially introduce bias in discussions with the study site. The pharmacokineticists, statisticians, programmers, and data managers, however, will need access to subject randomization during the course of the single dose escalation and repeat dose escalation portions of the study for analysis purposes to support dose adjustments and escalations. Other GSK staff may be included in discussions around dose adjustments and progression if it is deemed necessary and relevant by the above mentioned GSK study team members.

During dosing of a specific cohort, the investigator or treating physician may unblind a subject's treatment assignment only in the case of an emergency, when knowledge of the study treatment is essential for the appropriate clinical management or welfare of the subject. Whenever possible, the investigator must first discuss options with the GSK medical monitor or appropriate GSK study personnel before unblinding the subject's treatment assignment. If this is impractical, the investigator must notify GSK as soon as possible, but without revealing the treatment assignment of the unblinded subject, unless that information is important for the safety of subjects currently in the study. The date and reason for the unblinding must be recorded in the electronic data capture system. *In this situation, the subject will be withdrawn from further treatment if the subject's treatment code is unblinded by the investigator or treating physician.* The primary reason for discontinuation (the event or condition which led to the unblinding) will be recorded in the electronic data capture system. GSK's Global Clinical Safety and Pharmacovigilance staff may unblind the treatment assignment for any subject with an SAE. If the SAE requires that an expedited regulatory report be sent to 1 or more regulatory agencies, a copy of the report, identifying the subject's treatment assignment, may be sent to the investigator in accordance with local regulations and/or GSK policy.

During the dose escalation safety review, the GSK clinical team and the investigator will review safety data in a blinded aggregate form. In the event of concern over a potential safety signal, the GSK clinical team and the investigator may review unblinded treatment assignments for the purposes of safety review and dose selection without study interruption. If a safety signal is determined to indicate findings in subjects who received GSK3342830, the findings will be escalated for assessment by the GSK safety team and actions taken as appropriate including review of study for possible halting of further dosing.

6.5. Packaging and Labeling

The contents of the label will be in accordance with all applicable regulatory requirements.

6.6. Preparation/Handling/Storage/Accountability

A description of the methods and materials required for preparation of GSK3342830 infusion and placebo infusion will be detailed in a Pharmacy Manual which will be accompanied by a Quality Agreement.

- Only subjects enrolled in the study may receive study treatment and only authorized site staff may supply or administer study treatment. All study treatments must be stored in a secure environmentally controlled and monitored (manual or automated) area in accordance with the labelled storage conditions with access limited to the investigator and authorized site staff.
- The investigator, institution, or the head of the medical institution (where applicable) is responsible for study treatment accountability, reconciliation, and record maintenance (i.e. receipt, reconciliation and final disposition records).
- Further guidance and information for final disposition of unused study treatment are provided in the Pharmacy Manual.
- Under normal conditions of handling and administration, study treatment is not expected to pose significant safety risks to site staff.
- A Material Safety Data Sheet or equivalent document describing occupational hazards and recommended handling precautions either will be provided to the investigator, where this is required by local laws, or is available upon request from GSK.

6.7. Compliance with Study Treatment Administration

When the individual dose for a subject is prepared from a bulk supply, the preparation of the dose will be confirmed by a second member of the study site staff.

Subjects will be dosed at the clinical unit and receive study treatment directly from the investigator or designee, under medical supervision. The date and time of each dose administered in the clinical unit will be recorded in the source documents. The dose of study treatment and study subject identification will be confirmed at the time of dosing by a member of the study site staff other than the person administering the study treatment.

GSK3342830 and placebo will be administered intravenously to subjects at the site. Administration will be documented in the source documents and recorded in the electronic case report form (eCRF).

6.8. Treatment of Study Treatment Overdose

GSK3342830 will be administered at the clinical unit, thus limiting the risk of overdose. In the unlikely event that an overdose with GSK3342830 should occur, the investigator must notify the sponsor promptly. There is no specific antidote for overdose with GSK3342830. In the event of a suspected overdose, it is recommended that the appropriate supportive clinical care should be instituted, as dictated by the subject's clinical status.

GSK does not recommend specific treatment for an overdose.

In the event of a suspected overdose the investigator should:

1. Contact the medical monitor
2. Closely monitor the subjects for AEs/SAEs and laboratory abnormalities until GSK3342830 can no longer be detected systemically (at least 1 day)
3. Obtain a plasma sample for PK analysis within 1 day from the date of the last dose of study treatment if requested by the medical monitor (determined on a case-by-case basis)
4. Document the quantity of the excess dose as well as the duration of the overdosing in the eCRF

Decisions regarding dose interruptions or modifications will be made by the investigator in consultation with the medical monitor based on the clinical evaluation of the subject.

